
D4.2. Sample size considerations. Using G*Power 3.1.9.2¹²⁴ we estimate that 15 participants/group will be required to detect *realistic and clinically meaningful effects of sleep extension* (based on data from our own studies evaluating weight loss or weight gain^{36,87,88} and to data from our own and other groups assessing the metabolic effect of sleep restriction^{17-19,24}) with >90% power using two-sided tests at the $\alpha=0.05$ level of significance in all primary and secondary outcomes listed below.

D4.2.1 Primary outcome

Insulin-mediated glucose Rd. We have found the average insulin-mediated glucose Rd during high-dose insulin infusion to be 59.1 $\mu\text{mol/kg FFM/min}$ in people with obesity with a day-to-day variability of 6.4 $\mu\text{mol/kg FFM/min}$ (mean \pm SD) ⁷⁶. Using this SD and assuming similar variance in the sleep restriction and extension groups, we estimate we will be able to detect a $\sim 7.9 \mu\text{mol/kg FFM/min}$ ($\sim 13\%$) difference between groups. This difference is smaller than the $\sim 20\%$ reduction in insulin-mediated glucose Rd observed after acute (1 to 7 d) sleep restriction^{17-19,24}.

D4.2.2 Secondary outcomes

24-h glucose area-under-the curve (AUC). We have found average 24h glucose AUC is 2650 mg/dl/24h in people with obesity with a day-to-day variability of $80 \pm 130 \text{ mg/dl/24h}$ (mean \pm SD). Using this SD and assuming similar variability in both groups, we estimate we will be able to detect a between group difference of $\sim 137 \text{ mg/dl/24h}$ ($\sim 5.2\%$). Five nights of sleep restriction increases average plasma glucose concentration by 11% over 10 h during the day¹²⁵. Two nights of sleep restriction increases postprandial breakfast plasma glucose AUC by 7.4% after breakfast¹²⁶.

24-h insulin AUC. We have found average 24-h insulin AUC is $818 \pm 333 \mu\text{U/ml/24h}$ in people with obesity with a day-to-day variability of $26 \pm 85 \mu\text{U/ml/24h}$ (mean \pm SD). Using this SD and assuming similar variability in both groups, we estimate we will be able to detect a between group difference of $\sim 90 \mu\text{U/ml/24h}$ ($\sim 11\%$). Five nights of sleep restriction increases average plasma insulin concentration by 29% over 10 h¹²⁵. Two nights of sleep restriction increases postprandial breakfast plasma insulin AUC by 52%¹²⁶.

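### D4.2 claims more than 90% power at 15 per group for every outcome, but its own inputs give that only for glucose Rd and about 80% for the two 24-h AUCs

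*Combined protocol and SAP*

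**What the plan says.** D4.2 opens with "we estimate that 15 participants/group will be required to detect" effects that the authors regard as realistic and clinically meaningful, "with >90% power using two-sided tests at the $\alpha=0.05$ level of significance in all primary and secondary outcomes listed below".

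The outcomes listed under that sentence are:

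- **Primary (D4.2.1), insulin-mediated glucose Rd.** The mean is 59.1 µmol/kg FFM/min, "in people with obesity with a day-to-day variability of 6.4". The step to a detectable difference of about 7.9 (13%) is made "Using this SD and assuming similar variance in the sleep restriction and extension groups".
- **Secondary (D4.2.2), 24-h glucose AUC.** Mean 2650, day-to-day variability 80 ± 130, detectable difference about 137 (5.2%).
- **Secondary (D4.2.2), 24-h insulin AUC.** Mean 818, day-to-day variability 26 ± 85, detectable difference about 90 (11%).
- **Gene expression (last paragraph of D4.2.2).** Variability about 30%, with at least 80% power for a difference of about 35%.

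Elsewhere, D4.1 specifies an ANCOVA of the post value on the pre value among completers, D2.3 randomises 25 per arm, D7.3 cites retention above 90% in earlier studies, and Table 2 plans for all 50 to complete the post-intervention admissions.

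**The concern.** One sentence assigns the same power, above 90%, to every outcome at 15 per group. The last outcome listed carries a lower figure (at least 80%), so the section already disagrees with itself. The ratios of difference to SD raise the same doubt: 7.9/6.4 = 1.23 for Rd, but 137/130 = 1.05 and 90/85 = 1.06 for the AUCs. At one sample size these cannot all correspond to the same power.

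Two further gaps concern the primary outcome. Power is given only at 15 per group, which is not the number randomised, and nothing explains the step to 25. The single SD offered for Rd is also not defined well enough to tie it to the residual SD of the planned ANCOVA.

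D5 relies on the sample size having adequate power, and a null result on any of these outcomes will be read against the D4.2 figures. A reader who takes 90% for the AUCs would overstate what a null at 15 per group excludes.

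**Working it through.** **Method.** Two-sample t-test, noncentral t, two-sided 0.05, n per group, df = 2n − 2, noncentrality = (difference/SD) × √(n/2). Losing one df to the ANCOVA covariate changes power by about 0.1 percentage point at 15 per group.

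**Step 1. Reproduce the plan's primary figure.** At n = 15, 7.9/6.4 = 1.234 gives power 90.4%. The difference detectable with 90% power is 1.226 × 6.4 = 7.85. The stated 7.9 therefore reproduces as a two-sided, 90%-power figure.

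**Step 2. Apply the same calculation to the other outcomes at 15 per group.** The standardised difference needed is 1.226 for 90% power and 1.060 for 80%.

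| Outcome | Stated difference / SD | Power at 15 per group | Difference at 80% | Difference at 90% |
|---|---|---|---|---|
| Glucose Rd | 7.9 / 6.4 | 90.4% | 6.8 | 7.85 |
| 24-h glucose AUC | 137 / 130 | 79.6% | 137.8 | 159 (159/2650 = 6.0%) |
| 24-h insulin AUC | 90 / 85 | 79.9% | 90.1 | 104 (104.2/818 = 12.7%) |
| Gene expression (reading 30% as an SD) | 35 / 30 | 86.9% | 31.8 | 36.8 |

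The two AUC differences match 80% power almost exactly. They look like 80% calculations placed under a 90% heading.

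**Step 3. Move to the numbers the trial expects.** Retention of 90% of 25 is 22.5, so retention above 90% means at least 23 per arm. The standardised difference for 90% power is 0.977 at 23 and 0.936 at 25. With the plan's SDs:

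| Outcome | Power for the stated difference, 23 / 25 per arm | 90%-power difference, 23 / 25 per arm |
|---|---|---|
| Glucose Rd | 98% / 99% | 6.3 / 6.0 |
| 24-h glucose AUC | 93.8% / 95.5% | 127 / 122 |
| 24-h insulin AUC | 94.0% / 95.6% | 83 / 80 |

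On the unexplained step from 15 to 25: a 40% loss would link them, 15/(1 − 0.4) = 25, but D7.3 and Table 2 point to little or no loss.

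**Step 4. Show what the undefined 6.4 does to Rd.** Let s be the SD of one measurement about a person's own mean and R the reliability of a single measurement. With measurement noise alone, the ANCOVA residual SD is s × √(1 + R), with R between 0 and 1.

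- If 6.4 is s, the residual SD is 6.4 to 6.4 × √2 = 9.05.
- If 6.4 is the SD of the difference between two repeats, s = 6.4/√2 = 4.53 and the residual SD is 4.53 to 6.4.

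| Residual SD | Power for 7.9 at 15 per group | at 23 per arm | at 25 per arm |
|---|---|---|---|
| 4.53 | 99.6% | >99.9% | >99.9% |
| 6.4 | 90.4% | 98% | 99% |
| 9.05 | 64% | 83% | 86% |

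The largest SD that keeps 90% power for 7.9 is 6.44 at 15 per group and 8.44 at 25 per arm. Drift over 4–6 weeks and varying response to sleep extension would add to either range. The documents give no figure for them.

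**The case against.** The strongest defence concerns the primary outcome, and much of it stands.

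- A reader might infer that a day-to-day SD is the wrong kind of input for a between-group comparison, or that 6.4 is a best case. The documents do not support this. Adjusting for baseline removes stable differences between people, so a repeat-measurement SD is a reasonable starting point. The AUC entries give day-to-day variability as a non-zero mean with an SD, which suggests repeat differences. If 6.4 is of that type, it is the upper end of the noise-only range. The insulin contrast of 333 between people against 85 day to day therefore does not show that the Rd input is too small.
- Even at SD 9.05, the roughly 20% effect that the plan cites for sleep restriction (0.20 × 59.1 = 11.8) has 93% power at 15 per group and 99% at 25.
- A reader might see 15 against 25 as a contradiction. It is not one: no power is stated for 25, and randomising more than the required number adds margin. What is missing is the explanation.
- A reader might fault the glucose benchmark, which "increases average plasma glucose concentration by 11% over 10 h during the day", for sitting beside a 24-h difference of 5.2%. The time base is openly stated. Spreading it over 24 h as 11% × 10/24 = 4.6% assumes no effect in the other 14 hours, so 4.6% is only a floor.

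None of this answers the AUC figures. They follow from the plan's own differences, SDs and sample size, without any outside assumption.

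**Conclusion.** The blanket power statement in D4.2 is wrong as written. At 15 per group it holds for glucose Rd (90.4%) but not for 24-h glucose AUC (79.6%) or 24-h insulin AUC (79.9%), and the plan's own gene-expression figure is only at least 80%. The AUC result rests solely on the plan's inputs and a two-sample t-test, the method that reproduces its primary figure.

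For Rd the conclusion is narrower. The 7.9 is correctly calculated but has no margin at 15 per group, and its link to the ANCOVA residual is not documented. Power for 7.9 at 15 per group is 64% at the top of one reading of 6.4 and at least 90% throughout the other, before any drift. The documents do not settle which reading applies.

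It would go too far to conclude that the trial is underpowered. With the plan's SDs, the 25 per arm randomised give 95% or more for all three stated differences (Rd and the two AUCs), and Rd still has 86% at SD 9.05. The error lies in what is claimed at 15 per group and in the absence of figures for the sample actually planned.

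**What to change.** In D4.2:

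1. Replace the blanket claim with the power each outcome has at 15 per group: 90% for Rd, about 80% for the two AUCs, and the existing figure of at least 80% for gene expression. Alternatively, keep 90% and restate the AUC differences as about 159 mg/dl/24h (6.0%) and 104 µU/ml/24h (12.7%).
2. Add power or detectable differences at the expected completers, 25 per arm and 23 per arm at 90% retention. With the plan's SDs, the 90%-power differences at 25 per arm are about 6.0 for Rd, 122 for glucose AUC and 80 for insulin AUC. Say in one sentence why 25 are randomised when 15 are described as required.
3. State whether 6.4 is a single-measurement SD or an SD of repeat differences. If this cannot be established, show Rd power under both readings. At 25 per arm that is 99% for 7.9 at SD 6.4 and 86% at SD 9.05. Note that neither reading includes drift over 4–6 weeks.

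The cost is a rewritten paragraph. No participants, visits or analyses are added. The only downside is that some stated figures become less favourable.

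### 24h glucose AUC (D4.2.2): the supporting benchmarks are not on the 24h scale, and the >90% power stated at 15 per group is not supported for this outcome

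*Combined protocol and SAP*

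**What the plan says.** Section D4.2 states that "15 participants/group will be required to detect" what it calls "realistic and clinically meaningful effects of sleep extension", with ">90% power using two-sided tests at the" 0.05 "level of significance in all primary and secondary outcomes listed below".

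The 24h glucose paragraph of D4.2.2 starts from a mean: "We have found average 24h glucose AUC is 2650 mg/dl/24h in people with obesity". It takes an SD of 130 mg/dl/24h from day-to-day variability, assumes the same variability in both groups, and gives a detectable between-group difference of about 137 mg/dl/24h (about 5.2%). Two literature effects follow at once: "Five nights of sleep restriction increases average plasma glucose concentration by 11% over 10 h during the day" and "Two nights of sleep restriction increases postprandial breakfast plasma glucose AUC by 7.4% after breakfast". Neither is converted to 24 h, and no sentence says how they bear on the 5.2%.

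Elsewhere, D2.3 randomizes 25 per group. D4.1 analyses only participants who complete the study. D7.3 cites retention above 90% in earlier studies. D5 repeats that the sample size has the power needed.

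**The concern.** The outcome is an area over 24 h. A percentage rise confined to 10 h, or to the hours after one meal, is a smaller percentage of the 24h area unless the remaining hours rise as well. Read next to 5.2%, 11% looks like about twice the detectable difference and 7.4% like about 1.4 times it. On a common time base that margin shrinks or disappears.

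What is at stake is the assurance attached to a named secondary outcome that also belongs to an Aim 1 hypothesis. If the power is overstated, a non-significant 24h glucose result would be judged against a sensitivity the plan has not shown.

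**Working it through.** **Inputs.** From D4.2 and D4.2.2: mean 2650, SD 130, difference 137 (all mg/dl/24h), 15 per group, two-sided alpha 0.05. From D2.3: 25 per arm. Completers: 25 x 0.90 = 22.5, taken as 22 per arm (assumption, from the retention figure in D7.3). Power is for a two-sample t test (noncentral t) with d = difference/SD, taking the SD of 130 as the plan does.

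**1. The plan's own figure.** 137/2650 = 5.17%, which matches the stated 5.2%. d = 137/130 = 1.054. Power at 15 per group is 79.6% by t, 82.3% by the normal approximation, and 79.5% with one degree of freedom given up for the ANCOVA covariate. A one-sided test gives 87.9%. None of these exceeds 90%. The 80%-power detectable difference at 15 per group is 137.8, so 137 appears to have been set at 80%. By contrast, the primary outcome (7.9/6.4 = 1.234) does give 90.4% at 15 per group.

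**2. Detectable difference at 90% power, SD 130.**

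| n per arm | Difference (mg/dl/24h) | % of 2650 |
|---|---|---|
| 15 | 159 | 6.0 |
| 22 | 130 | 4.9 |
| 25 | 122 | 4.6 |

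**3. The 10 h benchmark on the 24h scale.** Let r be mean glucose in the 10 h window divided by mean glucose in the other 14 h, and let x be the percentage rise in those 14 h. Neither is given in the documents.

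- With x = 0: 24h effect = 11% x 10r/(10r + 14).
- With r = 1: 24h effect = (11 x 10 + x x 14)/24.

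| Assumption | 24h effect | mg/dl/24h | Power, 15 per group | 22 per arm | 25 per arm |
|---|---|---|---|---|---|
| r = 1, x = 0 | 4.58% | 121.5 | 69.5% | 85.7% | 89.9% |
| r = 1.2, x = 0 | 5.08% | 134.5 | 78.1% | 91.8% | 94.8% |
| r = 1.3, x = 0 | 5.30% | 140.4 | 81.4% | 93.8% | 96.2% |
| r = 1, x = 1% | 5.17% | 136.9 | 79.5% | 92.7% | 95.4% |

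To reach 90% power at 15 per group, the 24h effect must be about 6.0%. That needs r of about 1.69 with no change elsewhere, or a rise of about 2.5% in the other 14 h on a flat profile.

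**4. The breakfast benchmark.** The plan gives no window length for the 7.4%, so the conversion cannot be done. The 5 h meal window in D2.5 is this trial's own AUC definition, not that of the cited study. An effect after one meal also says nothing about the two later meals or the night.

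**The case against.** Four points on the other side carry weight.

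- **4.6% depends on its assumptions.** Hours that were not measured are not hours without an effect, and with three meals a day a flat profile is doubtful. A 1% rise in the other 14 h, or a daytime ratio between 1.2 and 1.3, already brings the effect to about 5.2%. This stands, and it is why a range is given. It does not rescue the claim at 15 per group, where every row of the table has power well below 90%.
- **The plan makes no explicit comparison for this outcome.** For the primary outcome it says that the detectable difference is smaller than the published effect. Here it only lists effects with their windows labelled, and the general statement about realistic effects in D4.2 cites other sources. This stands as to wording. Still, these two figures are the only outside support offered for this outcome, and they are placed directly after the 5.2%.
- **The trial randomizes 25 per arm, and Table 2 plans for all 50 to finish.** This stands. A reader might infer that the trial is underpowered for its own benchmark. The documents do not support that: even on the least favourable row, power is about 90% at 25 per arm.
- **It is a secondary outcome.** This stands and limits the severity.

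A reader might also multiply 7.4% by 5/24, get 1.5%, and conclude that power is negligible. That borrows a window from this trial for a study whose window is not stated, and treats one meal as the whole day. The breakfast figure can be set aside as support, but it is not evidence of a tiny effect.

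**Conclusion.** The time bases do not match, and the power stated for 24h glucose AUC at 15 per group is wrong on the plan's own inputs: 137 has about 80% power, not more than 90%. Put on the 24h scale, the 10 h benchmark is about 4.6% under a flat profile with no effect elsewhere, and 5.1 to 5.3% if daytime glucose is 1.2 to 1.3 times the rest of the day. Power at 15 per group is then about 70% and 78 to 81%. At 25 per arm, power for 4.6% is about 90%; with 22 completers per arm it is about 86%. The breakfast effect does not support a 24h difference either way.

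These figures rest on the SD of 130 applying to the between-group comparison, as the plan assumes, and on profile assumptions that the documents do not give. The fault lies in the justification and the stated power. It does not show that the planned enrolment is inadequate or that the outcome is badly chosen. Severity: minor.

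**What to change.** Rewrite the 24h glucose paragraph of D4.2.2:

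1. Express the 10 h benchmark on the 24h scale, with the assumptions and the range: about 4.6% if the profile is flat and the other hours do not change, about 5.1 to 5.3% if daytime glucose is 1.2 to 1.3 times the rest.
2. Remove the breakfast figure as support for the 24h AUC.
3. Exempt this outcome from the general statement of more than 90% power at 15 per group. State instead that 137 has about 80% power at 15 per group, and that the 90%-power detectable difference is about 159 (6.0%) at 15 per group, 130 (4.9%) at 22 per arm and 122 (4.6%) at 25 per arm.

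The sized secondary outcome, the sampling and the enrolment stay as they are. The cost is one paragraph and a less favourable stated power at 15 per group.
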